5.1.1. Protocol Deviations

Protocol deviations (PDs) will be tracked by the study team throughout the conduct of the study in accordance with the Protocol Deviation Management Plan. PDs will be categorized to Major PD and Minor PD.

Statistical Analysis Plan for Protocol ABSK-021-301

PD data and their categories will be reviewed and agreed before freezing the database for each planned analysis.

All protocol deviations will be listed for the ITT. All major and minor protocol deviations will be summarized by treatment group based on PD Categories.

The number and percentage of patients in the ITT with any protocol deviation will be tabulated for the following categories by deviation category (as specified in the study deviation specification document) and by treatment group.

- Patients with at least one protocol deviation
- Patients with at least one major protocol deviation
- Patients excluded from per-protocol analysis set due to major PD

All protocol deviations will be listed with flags for severity (major, minor).

5.2. Demographics and Baseline Characteristics

All demographic data such as age, age groups, gender, race, and ethnicity will be summarized by treatment group for the ITT analysis set. Standard descriptive statistics will be presented for the continuous variables of:

- Age (years);
- Baseline weight (kg);
- Height (cm);
- BMI (kg/m²).

The frequencies and percentages of patients will be presented for the categorical variables of subgroups as described in [Section 4.1.2](#), plus the following group.

- Unresectability (Yes vs. No vs. Unable to confirm)

Other baseline measurements (e.g., PRO, lab, vital signs, ECG, etc.) will be summarized together with the post-baseline measurements.

5.3. Diagnosis of Tumor and Baseline Disease Characteristics

These data will be summarized by treatment group and overall for the ITT. A listing will be prepared as well.

Standard descriptive statistics will be presented for the continuous variables of:

- Time from initial diagnosis (years) [calculated as (date of informed consent – date of initial diagnosis + 1)/365.25, partial date of initial diagnosis will be imputed per rules in the [Appendix 1](#) of Section 11.1 before calculation];
- Time from current diagnosis (days) [calculated as (date of informed consent – date of current diagnosis + 1), partial date of current diagnosis will be imputed per rules in the [Appendix 1](#) of Section 11.1 before calculation];

The frequencies and percentages of patients will be presented for the categorical variables of:

- Initial Diagnosis

Statistical Analysis Plan for Protocol ABSK-021-301

- TGCT Type
- Current Diagnosis
- Current Tumor Location
- Metastatic (Yes, No)
 - If Yes, Location of Metastasis

These categories in each item will be based on subcategories specified in the corresponding CRF page unless stated otherwise.

5.4. Medical History

Medical history will be coded using MedDRA Version 25.1 or higher. Medical history data will be summarized by randomized treatment group.

5.5. Prior, Concomitant and Subsequent Therapy

5.5.1. Definition and Classification

Prior and concomitant and subsequent therapy includes any medications for treating both cancer and non-cancer conditions, surgeries, and radiotherapies that patients received prior to the study start, during study treatment and throughout study follow-up period. Medications will be coded to Anatomical Therapeutic Classification (ATC) and preferred name (PN) using the latest version of World Health Organization Drug Dictionary (WHODD). Non-medication therapies will be coded using MedDRA.

Prior therapies are those medications, surgeries and radiotherapies received prior to the first dose of the study drug and ending before the first study drug dose of Part 1. Concomitant therapies are defined as of those were started on or after the first dose of the study drug but prior to the last dose of the study drug at the time of data cut-off + 30 days or started prior to the study drug and were ongoing during the treatment period. Subsequent anti-cancer therapies are those that ~~were~~ started after the last dose of the study drug. Medications, surgeries and radiotherapies with incomplete start and/or end dates will be imputed for classification of prior, concomitant and subsequent according to [Appendix 1](#). Those with incomplete start and/or end dates will be assumed to be concomitant if it cannot be shown that the medication, surgery or radiation therapy was not taken during the treatment period. For any incomplete onset or end date, the imputed date and raw date will be listed.

5.5.2. Prior Anti-Cancer Therapy

The number and percentage of patients with any prior systemic anti-cancer therapy, intent, line of therapy, type of therapy, the best response, reason for discontinuation and disease progression or recurrence will be summarized by treatment group for the ITT analysis set. The duration of last prior systematic therapy and time from the date of last prior systemic therapy to the first dose of study drug may be descriptively summarized.

Statistical Analysis Plan for Protocol ABSK-021-301

The number and percentage of patients under different number of prior surgery (i.e., none, ≥ 1 , ≥ 2 , ≥ 3 etc.) and patients with or without radiation therapy will be summarized by treatment group and overall.

5.5.3. Prior and Concomitant Medication

The number and percentage of patients receiving any prior medication and concomitant medication will be summarized by treatment group and overall, by ATC (level 2) and PN for the ITT analysis set. If a patient took a medication multiple times, the patient will only be counted once within ATC and PN within ATC, respectively. The summary will be presented in a descending order of incidence of the ATC and PN within ATC across patients overall.

The concomitant medication used for adverse events of clinical interest (defined in [Section 7.2.3](#)) will be summarized by ATC (Level 2) and PN, separately.

Listings will be produced for prior and concomitant medication, prior and concomitant non-medication therapies with flags indicating prior or concomitant.

5.5.4. New Anti-Cancer Therapy

The number and percentage of patients receiving any new anti-cancer surgery, surgery location, surgery intent, pathological results after surgery and recurrence will be summarized by treatment group and overall.

Patients receiving any other new anti-cancer therapies other than surgery will be listed.

5.6. Study Drug Administration

This study drug administration summary will include all relevant safety data obtained throughout the on-treatment period. The summary will be prepared for each respective group within each planned analysis stage as outlined in [Table 4.7](#) based on the Safety Analysis set.

Duration of drug exposure, cumulative actual dose, actual dose intensity (ADI), relative dose intensity (RDI), percentage of intended dose (PID), and number of patients with dose reductions, interruptions and their reasons will be descriptively summarized and listed for the Safety Analysis Set. Furthermore, the percentage of intended dose (PID) will be summarized by the planned visit.

Details of the derivations and summaries for the SST are provided in the following sections.

5.6.1. Duration of Study Drug Exposure

Exposure to the study drug will be defined as:

- Total duration of exposure (day) = min (last dose date, date of death, date of cut-off) – first dose date + 1
- Actual duration of exposure (day) = total planned exposure – total duration of dose interruptions

Statistical Analysis Plan for Protocol ABSK-021-301

The total and actual duration of exposure for ABSK021 will be summarized descriptively. The number and percentage of patients will be summarized by following categories of duration of drug exposure:

- < 1 month, $\geq 1 - < 3$ months, $\geq 3 - < 6$ months, $\geq 6 - < 9$ months, $\geq 9 - < 12$ months, $\geq 12 - 18$ months, $\geq 18 - 24$ months, ≥ 24 months
- ≥ 1 month, ≥ 3 months, ≥ 6 months, ≥ 9 months, ≥ 12 months, ≥ 18 months, ≥ 24 months

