28. The PROMIS Physical Functioning Scale and the EQ-5D-5L Health Scale will be assessed during the screening period (within 14 days prior to randomization), on C1D1 (-1 day), C2D1 (± 7 days), C3D1 (± 7 days), C4D1 (± 7 days), C5D1 (± 7 days), C6D1 (± 7 days) and C7D1 (± 7 days), respectively. C1D1 assessments should be completed prior to dosing. The mean score of evaluations during the screening period (within 14 days prior to randomization) and on C1D1 will be used as baseline. The PROMIS Physical Functioning Scale includes two different sets of topics for the upper and lower extremities. Items assessing lower extremity function will be used for patients with lower extremity tumors, and the items for assessing upper extremity function will be used for patients with upper extremity tumors. On visit days when scales are required, including the screening period, it is recommended to be completed before any invasive clinical procedure is performed. Even if a patient experiences disease progression or discontinues treatment, PROMIS Physical Functioning Scale and the EQ-5D-5L Health Scale are recommended to be completed from baseline up to week 25.

29. NCI-PRO-CTCAE will be assessed during the screening period (within 14 days prior to randomization), on C1D1 (-1 day), C1D8(± 1 days), C1D15 (± 1 days), C1D22 (± 1 days), C2D1 (± 2 days), C2D8(± 2 days), C2D15 (± 2 days), and C2D22 (± 2 days), C3D1 (± 7 days), C4D1 (± 7 days), C5D1 (± 7 days), C6D1 (± 7 days), C7D1 (± 7 days), and EOT visit respectively.
30. Patient who completed the C7D1 visit of Part 1 will be further confirmed by the investigator whether to enter Part 2 and receive treatment with open-label ABSK021. Patients need to meet eligibility criteria to continue in Part 2. The investigator will comprehensively evaluate the benefits and risks of the patient entering Part 2, and make the final decision based on the principle of maximizing the patient's benefit-risk ratio. In principle, a maximum of 28 days is allowed from the end of C7D1 follow-up in Part 1 to entry into Part 2.

Table 2: Schedule of Events - Part 2

Study Procedure	Cycle 1 ¹	Cycle 2	Cycle 3	Cycle 4 ²	Cycle 7	End of Treatment Visit (EOT Visit) ³	Safety Follow-up ⁴	Progression Follow-up ⁵
	C1D1 (- 2 days)	C2D1 (± 7 days)	C3D1 (± 7 days)	C4D1 (± 7 days)	C7D1 (± 7 days)			
	Week 25	Week 29	Week 33	Week 37	Week 49			
Part 2 eligibility confirmation ¹	X							
Physical examination/ECOG score ⁶	X	X	X	X	X	X		
Vital Signs ⁷	X	X	X	X	X	X		

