23. Patients should complete BPI-Worst-Pain-NRS and Worst-Stiffness-NRS on C1D1 (at least 4 of 7 consecutive days within ± 7 days), C2D1 (at least 4 of 7 consecutive days within ± 7 days), C3D1 (at least 4 of 7 consecutive days within ± 7 days), C4D1 (at least 4 of 7 consecutive days within ± 7 days) and C7D1 (at least 4 of 7 consecutive days within ± 7 days). If the assessment to be performed at Part 2 C1D1 visit has been done at Part 1 C7D1 visit or the latest visit before P2-C1D1, with an interval of no more than 7 days, repeated assessments are not required on C1D1 of Part 2. On the days when a Numerical Rating Scale is required, it is recommended to be completed prior to any invasive clinical procedure.
24. The PROMIS Physical Functioning Scale and the EQ-5D-5L Health Scale will be assessed on C1D1 ($+ 7$ days), C2D1 (± 7 days), C3D1 (± 7 days), C4D1 (± 7 days), and C7D1 (± 7 days), respectively. The PROMIS Physical Functioning Scale includes two different sets of topics for the upper and lower extremities. Items assessing lower extremity function will be used for patients with lower extremity tumors, and the items for assessing upper extremity function will be used for patients with upper extremity tumors. If the assessment to be performed at Part 2 C1D1 visit has been done at Part 1 C7D1 visit or the latest visit before P2-C1D1, with an interval of no more than 7 days, repeated assessments are not required on C1D1 of Part 2. On visit days when scales are required, it is recommended to be completed before any invasive clinical procedure is performed.
25. Patient who completed the C7D1 visit of Part 2 will be further confirmed by the investigator whether to enter Part 3 and continue to receive treatment with open-label ABSK021. Patients need to meet eligibility criteria to continue in Part 3. The investigator will comprehensively evaluate the benefits and risks of the patient entering Part 3, and make the final decision based on the principle of maximizing the patient's benefit-risk ratio. In principle, a maximum of 28 days is allowed from the end of C7D1 follow-up in Part 2 to entry into Part 3.

Table 3: Schedule of Events - Part 3

Study Procedure	Cycle 1 ¹	Cycle 4	Cycle 7	Cycle 13 ²	≥ Cycle 19	End of Treatment Visit (EOT Visit) ³	Safety Follow-up ⁴	Progression Follow-up ⁵
	C1D1 (- 2 days)	C4D1 (± 7 days)	C7D1 (± 7 days)	C13D1 (± 14 days)	≥ C19D1 (± 14 days)			
	Week 49	Week 61	Week 73	Week 97	≥ Week 121			

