5.1.2 ABSK021 Administration

In Part 1, patients in the ABSK021 treatment group will receive 25 mg/capsule of ABSK021, 2 capsules once daily, with a total daily dose of 50 mg; the drug can be taken with or without food; patients will receive repeated oral doses in 28-day treatment cycles until completion of 24 weeks of dosing or withdrawal from the study. Patients who complete treatment and follow-up in Part 1 (i.e., complete 24 weeks of dosing and Week 25 follow-up including MRI) and meet eligibility criteria will be eligible to continue in Part 2 or end of treatment (For patients who have not completed dosing and follow-up due to imaging disease progression, please refer to Section 4.3.1).

In Part 2, all patients will receive open-label ABSK021 2 capsules once daily at a total daily dose of 50 mg. The drug can be taken with or without food (If a patient has dose modification in Part 1, the patient will continue to be administered at the modified dose in Part 2). All patients will receive treatment with ABSK021 until completion of 24 weeks of dosing or withdrawal from the study.

In Part 3, all patients will continue to receive open-label ABSK021 once daily until any of the following events occurs: disease progression, experiencing unacceptable toxicity, withdrawal of informed consent form, commercialization of the study drug for the treatment of TGCT approved by the local regulatory authorities, decision by the sponsor to terminate the study, or until 2 years after the last patient enters Part 3, whichever occurs first. The starting dose in Part 3 for an individual patient will be determined by the dose he/she received at the end of Part 2.

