5.4 Treatment duration

The Part 1 study consists of a screening period (within 28 days prior to randomization) and a treatment period of 6 cycles (28 days/cycle, 24 weeks in total). The primary endpoint analysis will be performed after the last patient has completed Week 25 follow-up and tumor assessments (including Investigator assessment and BIRC assessment).

The Part 2 study consists of a treatment period of 6 cycles (28 days/cycle, 24 weeks in total). Patients who complete Part 2 treatment will be eligible to enter Part 3 to continue a longer period of treatment and safety follow-up.

Part 3 is an extension treatment phase. All patients will continue to receive open-label ABSK021 continuously (28 days per cycle) until any of the following events occur: disease progression, experiencing unacceptable toxicity, withdrawal of informed consent form, commercialization of the study drug for the treatment of TGCT approved by the local regulatory authorities, decision by the sponsor to terminate the study, or until 2 years after the last patient enters Part 3, whichever

occurs first.

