5.6.2. Study Drug Dose Intensity

Actual Cumulative Dose

Actual cumulative dose is defined as the total dose of the medication given during the study treatment exposure. All doses, including unscheduled doses, will be included in the calculation.

Actual cumulative dose (mg) = sum of (actual dose * actual frequency * duration per dose)

Dose Intensity and Relative Dose Intensity

Planned dose intensity (PDI) is defined as follows:

- $PDI \text{ (mg/ day)} = \text{Assigned treatment dose arm (i.e., total dosage per day)}$

Actual dose intensity (ADI) is defined as follows:

- $ADI \text{ (mg/ day)} = \text{Actual cumulative dose (mg)} / \text{Actual duration of exposure (day)}$

Relative dose intensity (RDI) is defined as follows:

- $RDI \text{ (\%)} = (ADI / PDI) * 100$

The number and percentage of patients in the following categories for RDI will be presented for: $> 0 - < 80\%$, $80\% - 100\%$, $> 100\% - \leq 120\%$, $> 120\%$.

Percentage of Intended Dose

Percentage Intended Dose (PID) will be calculated as:

- $(\text{Actual cumulative dose} / \text{Intended cumulative dose}) * 100$

Intended cumulative dose is defined as planned dose intensity * total duration of exposure.

The number and percentage of patients in the following categories for PID will be presented for: $> 0 - < 80\%$, $80\% - 100\%$, $> 100\% - \leq 120\%$, $> 120\%$.

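### In the safety columns that cross Parts, total exposure and intended dose count the undosed days between Parts, which lowers the percentage of intended dose and can move patients up an exposure category

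*SAP*

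**What the plan says.** SAP 5.6.1 takes total duration of exposure from "min (last dose date, date of death, date of cut-off", subtracts the first dose date and adds one day. Actual duration is "total planned exposure – total duration of dose interruptions", and its first term is not defined.

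SAP 5.6.2 states: "Intended cumulative dose is defined as planned dose intensity * total duration of exposure". Planned dose intensity is "Assigned treatment dose arm (i.e., total dosage per day". PID is the actual cumulative dose divided by the intended cumulative dose.

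SAP 5.6 applies these summaries to every group in Table 4.7. Three of those groups cross a Part boundary: ABSK021 P1-P3, Switched to ABSK021 P2+P3, and All ABSK021 Treated P1-P3.

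On the protocol side, section 5.1.2 gives "2 capsules once daily, with a total daily dose of 50 mg", and section 5.4 gives Part 1 a "treatment period of 6 cycles (28 days/cycle, 24 weeks in total", with the same length for Part 2. Table 1 footnote 30 says that, in principle, "a maximum of 28 days is allowed from the end of C7D1 follow-up in Part 1 to entry into Part 2". Table 2 footnote 25 has the matching sentence for the next step: "a maximum of 28 days is allowed from the end of C7D1 follow-up in Part 2 to entry into Part 3". Dosing restarts on C1D1 of the new Part (Table 2 footnote 1, Table 3 footnote 1).

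**The concern.** Between the end of dosing in one Part and the first dose of the next, the protocol plans no dose. The SAP's span still counts those days as exposure, and the PID denominator counts them as days on which the full dose was intended. Nothing in SAP 5.6.1 or 5.6.2 takes them out.

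Two reported outputs are affected. PID falls below 100% for a patient who missed nothing, because of visit scheduling. The months-of-exposure categories (six, nine, twelve months and so on) can count a patient in a band that the dosing days do not reach. SAP 5.6 also asks for PID by planned visit. If that is calculated cumulatively, which the SAP does not say, PID would dip just after each transition and could be misread as missed dosing.

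**Working it through.** The plan states no PID or exposure figure, so there is none to reproduce. Its day count is consistent: 6 × 28 = 168 dosing days per Part, Week 25 target Day 169, and Week 49 target Day 337 (SAP Table 4.2).

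**Formula.** Take a patient on 50 mg throughout who takes every planned dose. The daily dose cancels, so PID = dosed days / (dosed days + undosed between-Part days).

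**Longest permitted gap.** The answer depends on when Part 1 dosing ends, and the protocol points two ways. Section 5.4 gives 24 weeks, which ends on Day 168. Table 1 footnote 22 (daily dosing until EOT), Table 2 footnote 19 (drug taken after the pre-dose sample at Part 2 C7D1) and Table 4 (pre-dose and 3-hour post-dose samples at C7D1) suggest dosing up to C7D1.

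| Case | Undosed days | PID, first day of Part 2 | PID, end of Part 2 |
|---|---|---|---|
| Dosed to C7D1 on Day 169, entry Day 197 | 27 | 170/197 = 86.3% | 337/364 = 92.6% |
| Dosed to Day 168, C7D1 Day 169, entry Day 197 | 28 | 169/197 = 85.8% | 336/364 = 92.3% |
| Dosed to Day 168, C7D1 Day 176 (+7 window), entry Day 204 | 35 | 169/204 = 82.8% | 336/371 = 90.6% |
| 14-day gap | 14 | 169/183 = 92.3% | 336/350 = 96.0% |
| 7-day gap | 7 | 169/176 = 96.0% | 336/343 = 98.0% |
| No gap | 0 | 100% | 100% |

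With two 28-day gaps, PID is 337/393 = 85.8% on the first day of Part 3 and 504/560 = 90.0% after 24 weeks of Part 3, so it recovers as treatment continues.

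**PID category.** To fall below 80% on the first day of Part 2 takes a 43-day gap: 169/212 = 79.7%, against 169/211 = 80.1% for 42 days. That is longer than any case above.

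**Exposure categories** (30.4375 days per month, SAP 4.2.3).

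- Six months is 6 × 30.4375 = 182.6 days. A 14-day gap plus one Part 2 dose gives a span of 168 + 14 + 1 = 183 days, or 6.01 months. The dosing days number 169, or 5.55 months.
- Twelve months is 12 × 30.4375 = 365.25 days. At the end of Part 2 there are 336 dosing days, or 11.04 months. A 29-day gap gives 365 days and stays below the cut; a 30-day gap gives 366 and crosses it. A 28-day gap gives 364 days, or 11.96 months, and does not cross. Thirty days is within the permitted window only if dosing ends on Day 168 and C7D1 is at least two days late.

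**The case against.** The strongest reply is that the plan expects little or no gap. Part 2 drug may be dispensed on the day the Part 1 C7D1 visit is completed (Protocol Table 2 footnote 19), SAP Table 4.2 gives Part 1 C7D1 and Part 2 C1D1 the same target day, and 28 days is a ceiling in principle. This stands. The documents give no distribution of gap lengths, so the figures above are upper cases, not expected values.

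A reader might infer that 83–91% is the general result, or that exposure is overstated for everyone. Neither is supported. Those figures need dosing to stop on Day 168, a C7D1 visit at the end of its window and the full 28 days, and a patient with no gap has no error.

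A reader might also take PID as the SAP's adherence measure and expect adherent patients to drop below 80%. The SAP does not call PID that. Because it uses the assigned dose, a sponsor-agreed reduction to 25 mg lowers it too. No gap within the permitted window takes the fully dosed patient out of the 80–100% band.

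It can be said that a first-to-last-dose span is an explicit definition and that actual duration nets out interruptions. But PID uses total duration, not actual duration, and the SAP does not say whether the between-Part gap is an interruption. Nor is the gap exposure in a pharmacological sense: 28 days is 672 hours, or 672/63.5 = 10.6 of the longest mean half-lives in Protocol 1.2.3.

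A last objection concerns the remedy. Summing first-to-last dose within each Part would hide real missed doses. Take a patient who stops after Day 134, restarts on Day 169 and doses to Day 336. The dosing days are 134 + 168 = 302. PID is 302/336 = 89.9% under the SAP, but 302/302 = 100% under a within-Part sum. This objection is right and shapes the fix.

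**Conclusion.** The point holds as a minor defect. For any patient with a gap, the two SAP formulas count between-Part days as exposure and as intended dosing in the three columns that cross Parts. At the longest permitted gap, a patient who took every dose shows PID of about 86% on the first day of Part 2 and 92–93% at its end, or 83% and 91% in the late-visit case with dosing ending on Day 168. The error is proportional to the gap and fades with longer treatment. The more tangible consequence is category shift, at six months with a 14-day gap and at twelve months with 30 days or more.

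This assumes no drug is taken in the gap and no dose reduction. It does not reach the Placebo P1 and ABSK021 P1 columns, which stop before the first Part 2 dose, nor any efficacy test. It also leaves the exposure-adjusted incidence rate in SAP 7.2.4 alone, since that has its own time-at-risk formula.

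**What to change.** In SAP 5.6.1 and 5.6.2, subtract the between-Part days, and only those, from total duration and from intended cumulative dose. They run from the day after the planned end of dosing in a Part to the day before the first dose of the next Part. The planned end is either that Part's C7D1 visit or its Day 168; the protocol passages on dosing up to C7D1 must be reconciled first, and the SAP should then name the one that applies. If the next Part starts before the planned end, as with early entry after progression, nothing is subtracted.

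Keep every undosed day before the planned end in the denominator, so that holds and missed doses near the boundary still lower PID. The patient in the example above then remains at 89.9%, and the fully dosed patient shows 100% (336 × 50 = 16,800 mg taken and intended at the end of Part 2). State that the gap is not a dose interruption, report its length as a separate descriptive line, and leave the AE time-at-risk formula unchanged.

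The cost is SAP wording and one more derivation from dates already collected. Reported exposure becomes slightly shorter.

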As of December 2022, a total of 49 TGCT patients were enrolled, including 37 patients in 50 mg dose group and 12 patients in 25 mg dose group. The updated data from 50 mg QD cohort as well as the preliminary data from 25 mg QD cohort had been read out. Tumor regression was observed across all evaluated patients, and median DOR was not reached in either cohort. The ORR was 77.4% (24/31, 95%CI: 58.90%-90.41%) in 50 mg QD cohort and 40% (4/10, 95%CI: 12.16%-73.76%) in 25 mg QD cohort by IRC based on RECIST v1.1 in response-evaluable analysis set. Average improvement of flexion range of knee at week 13 from baseline was 30.2 degrees (n=13, range: 2, 105) in 50 mg QD and 4.8 degrees (n=5, range: -12, 24) in 25 mg QD. These updated efficacy data showed significant anti-tumor effects of ABSK021 continuous dosing, especially in 50 mg QD cohort.

As of December 2022, the median treatment duration were 9.3 months and 6.2 months in 50mg and 25 mg QD cohort, respectively. Both 25mg QD and 50mg QD dosing of ABSK021 had

favorable safety and tolerability profile in TGCT patients. Most TEAEs were Grade 1 or 2 in both cohorts. No hair color changes or serious liver injuries were reported in either cohort. TEAE incidences were 91.7% (11/12) in 25 mg QD cohort and 94.6% (35/37) in 50 mg QD cohort. No drug-related serious TEAEs were reported in both cohorts. A total of 15 patients (15/49, 30.6%) have reported TEAEs leading to interruption of treatment, including 1 patient (1/12, 8.3%) in 25 mg QD cohort and 14 patients (14/37, 37.8%) in 50 mg QD cohort. But most of them were able to recover quickly and patients restarted the treatment of study drug within 1 month. Most common TEAEs ($\geq 20\%$) in both cohorts include LDH increase (37/49, 75.5%), CPK increase (33/49, 67.3%), α -HBDH increase (31/49, 63.3%), AST increase (21/49, 42.9%), amylase increase (13/49, 26.5%), ALT increase (12/49, 24.5%), pruritus (10/49, 20.4%) and rash (10/49, 20.4%). Due to the median duration of treatment in the 50 mg QD cohort is much longer than that in the 25 mg QD cohort, any comparison between these two dose levels should be interpreted with caution.

ABSK021-102 study has been completed and the clinical pharmacology data are detailed in 1.2.3 below. Efficacy data are not applicable in healthy subjects, and safety data are summarized as below:

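### SAP 5.6.1 builds actual exposure on an undefined planned length, so relative dose intensity is understated for patients who stop early

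*SAP*

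**What the plan says.** SAP 5.6.1 gives two durations. The first comes from actual dates: "Total duration of exposure (day) = min (last dose date, date of death, date of cut-off", counted from the first dose. The second opens with "Actual duration of exposure (day) = total planned exposure" and subtracts the total length of dose interruptions. Neither 5.6.1 nor 5.6.2 says what the planned term means. Both durations are to be summarised.

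SAP 5.6.2 then defines:
- planned dose intensity (PDI): "Assigned treatment dose arm (i.e., total dosage per day", which is 50 mg/day for ABSK021;
- ADI: actual cumulative dose divided by actual duration of exposure;
- RDI: ADI over PDI, as a percentage;
- PID: actual cumulative dose over intended cumulative dose, where "Intended cumulative dose is defined as planned dose intensity * total duration of exposure".

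RDI and PID are tabulated in the same four categories, the lowest being below 80%. SAP 5.6 asks for these summaries for every group in Table 4.7. Some of those groups pool Parts 1 to 3 up to the data cut-off, and they are part of the primary analysis. Protocol 7.4.3 names RDI among the exposure summaries; it does not name PID.

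**The concern.** The two lines of 5.6.1 rest on different bases. If the planned term means the scheduled length of Part 1, a patient who stops early has an actual exposure longer than the total exposure, which is impossible. The inflated denominator passes into ADI and RDI, so stopping early is reported as low dosing. For the groups that run into Part 3, no scheduled length exists and the formula cannot be computed without a rule the SAP does not give.

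At stake are the actual-duration table and the RDI table. Some early stoppers should be expected: the sample size allows for about 15% dropout, although dropout and stopping treatment are not the same event. The sponsor also relies on this kind of figure. Protocol 1.2.2 cites the proportion of Phase 1 patients with relative dose density between 80% and 120% as evidence of good compliance and tolerability.

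**Working it through.** The documents give no numerical RDI to reproduce, so the SAP definitions are applied to illustrative Part 1 patients.

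**Inputs**
- Daily dose 50 mg (Protocol 5.1.2: "2 capsules once daily, with a total daily dose of 50 mg"), so PDI = 50 mg/day.
- Planned Part 1 length: "treatment period of 6 cycles (28 days/cycle, 24 weeks in total" (Protocol 5.4), so 6 × 28 = 168 days.
- Stop days and hold lengths are assumed for illustration.

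**Formulas**, with *d* the total duration, *h* the days held, and full dose on every day not held:
- cumulative dose = 50 × (d − h)
- literal reading: actual duration = 168 − h, so RDI = 100 × (d − h)/(168 − h)
- with total duration in place of the planned term: actual duration = d − h, so RDI = 100 × (d − h)/(d − h) = 100%
- PID = 100 × (d − h)/d

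| Patient | Cumulative dose | Actual duration, literal | RDI, literal | RDI, total duration | PID |
|---|---|---|---|---|---|
| Stops day 84, no hold | 4200 mg | 168 days | 84/168 = 50.0% | 100.0% | 100.0% |
| Stops day 56, no hold | 2800 mg | 168 days | 56/168 = 33.3% | 100.0% | 100.0% |
| Stops day 84, 14 days held | 3500 mg | 154 days | 70/154 = 45.5% | 100.0% | 70/84 = 83.3% |
| Completes 168 days, 28 held | 7000 mg | 140 days | 100.0% | 100.0% | 140/168 = 83.3% |
| Completes, 25 mg after day 84, no hold | 6300 mg | 168 days | 75.0% | 75.0% | 75.0% |

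**Category boundary.** For an uninterrupted full-dose patient, literal RDI is below 80% when d < 0.8 × 168 = 134.4, that is, when the patient stops before about day 135.

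**Beyond Part 1.** If 168 days were kept as the planned length, 336 full-dose days (16,800 mg) would give an ADI of 100 mg/day and an RDI of 200%. Part 3 is open-ended, so no other fixed value is available.

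The first three rows show the error, and replacing the term removes it. The fourth row reads 100% under both readings, so that result does not come from the planned term.

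**The case against.** The strongest reply is that this is a drafting slip that would not survive programming. The SAP tabulates exposure out to 24 months and beyond and pools Parts 1 to 3, where a fixed planned length cannot be used. Total duration is defined one line earlier and already serves PID, so it is the natural substitute. This is a fair reason to treat the point as small. It does not remove it: the text as written gives a wrong figure in Part 1, where 168 days is available and plausible, and otherwise leaves the programmer to choose.

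A reader might go further and infer that RDI is also defective because it can read 100% despite long holds. That looks serious when Phase 1 recorded treatment-interrupting events in "14 patients (14/37, 37.8%) in 50 mg QD cohort". The documents do not support this as an error:
- It follows from removing held days from the denominator and occurs under either reading of the planned term.
- Leaving out held days can be a deliberate measure of dose intensity while on drug. It still registers reductions, as the 75% in the last row shows.
- Holds are captured elsewhere: PID on total duration in the same categories and by planned visit, both durations, the interruption counts and reasons in 5.6.3, and adverse events leading to interruption in 7.2.4.
- The 37.8% counts patients, not days held. Protocol 1.2.2 adds that treatment was mostly restarted within a month. In a 168-day completer, PID drops below 80% only when holds exceed 0.2 × 168 = 33.6 days.

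What stands from this side is the need for a label, since RDI and PID share categories and can place one patient differently without explanation.

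**Conclusion.** The formula is wrong as written. Its starting term is undefined, conflicts with the line above and has no fixed value in the pooled Part 1 to 3 groups. Taken literally in Part 1, it understates ADI and RDI for early stoppers: 50% instead of 100% for an uninterrupted stop on day 84, and 45.5% instead of 100% with a 14-day hold (PID 83.3%). Those sizes assume 168 planned days, full dose on every day not held, and the stop days and holds chosen above. How many patients would be affected cannot be derived from the documents.

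Severity is minor. The effect is confined to descriptive exposure tables in the Safety Analysis Set. No efficacy test, significance level or sample size depends on them.

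**What to change.** In SAP 5.6.1, replace *total planned exposure* with *total duration of exposure* in the formula for actual duration. In 5.6.2, keep RDI as ADI over PDI and add a footnote to the tables: RDI leaves out interruption days and so describes mean dose on dosing days relative to plan, while PID includes those days.

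RDI should not be redefined as cumulative dose over PDI times total duration. That is algebraically the existing PID, so the same number would be printed twice, the on-drug intensity measure would be lost, and RDI would no longer equal ADI over PDI.

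The cost is one phrase and one footnote, settled before the exposure tables are programmed. No data collection changes.
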